9.2 Agent Ordering and Agent Accountability

NCI supplied agents may be requested by the Principal Investigator (or their authorized designee) at each participating institution. Pharmaceutical Management Branch (PMB) policy requires that agent be shipped directly to the institution where the patient is to be treated. PMB does not permit the transfer of agents between institutions (unless prior approval from PMB is obtained.) The CTEP assigned protocol number must be used for ordering all CTEP supplied investigational agents. The responsible investigator at each participating institution must be registered with CTEP, DCTD through an annual submission of FDA form 1572 (Statement of Investigator), Curriculum Vitae, Supplemental Investigator Data Form (IDF), and Financial Disclosure Form (FDF). If there are several participating investigators at one institution, CTEP supplied investigational agents for the study should be ordered under the name of one lead investigator at that institution.

9.3 Clinical Drug Request

Active CTEP-registered investigators and investigator-designated shipping designees and ordering designees can submit agent requests through the PMB Online Agent Order Processing (OAOP) application. Access to OAOP requires the establishment of a CTEP Identity and Access Management (IAM) account and the maintenance of an "active" account status and a "current" password. For questions about drug orders, transfers, returns, or accountability, call or email PMB any time. Refer to the PMB's website for specific policies and guidelines related to agent management.

9.4 Agent Inventory Records

The investigator, or a responsible party designated by the investigator, must maintain a careful record of the receipt, dispensing and final disposition of all agents received from the PMB using the appropriate NCI Investigational Agent (Drug) Accountability Record (DARF) available on the CTEP forms page. Store and maintain separate NCI Investigational Agent Accountability Records for each agent, strength, formulation and ordering investigator on this protocol.

10.0 CRITERIA FOR REMOVAL FROM PROTOCOL THERAPY AND OFF STUDY CRITERIA

10.1 Criteria for Removal from Protocol Therapy

- a) Clinical (including physical examination or serum tumor markers) or radiographic evidence of progressive disease (See [Section 12](#)).
- b) Adverse Events requiring removal from protocol therapy (See [Section 6](#)).
- c) Refusal of further protocol therapy by patient/parent/guardian
- d) Non-compliance that in the opinion of the investigator does not allow for ongoing participation.
- e) Physician determines it is not in the patient's best interest.
- f) Repeated eligibility laboratory studies (CBC with differential, bilirubin, ALT (SGPT) or serum creatinine) are outside the parameters required for eligibility prior to the start of XL184 (See [Section 8.1](#)).
- g) Study is terminated by Sponsor.
- h) Pregnancy

Patients who are removed from protocol therapy during cycle 1 should continue to have the required observations in [Section 8.1](#) until the originally planned end of the cycle or until all adverse events have resolved per [Section 13.4.4](#), whichever happens LATER. The only exception is with documentation of the patient's withdrawal of

consent. Patients who are removed from protocol therapy in subsequent cycles should have the necessary observations to ensure adequate clinical care.

Patients who are off protocol therapy are to be followed beginning 30 days, 6 months, and annually (\pm 30 days) following the last dose of investigational agent until they meet the criteria for Off Study (see [Section 10.2](#)). Ongoing adverse events, or adverse events attributed to protocol therapy that emerge during the follow up period after the patient is removed from protocol therapy must be followed and reported via RAVE and CTEP-AERS (if applicable). Follow-up data will be required unless consent is withdrawn.

10.2 Off Study Criteria

- a) Death.
- b) Lost to follow-up.
- c) Withdrawal of consent for any further required observations or data submission.
- d) The fifth anniversary of study entry.

11.0 STATISTICAL AND ETHICAL CONSIDERATIONS

11.1 Sample Size and Study Duration

Parts of the Study:

Part A: Patients with relapsed or refractory solid tumors including CNS tumors and excluding patients with medullary thyroid cancer

Part B: Patients with medullary thyroid cancer (MTC)

*A minimum of 2 evaluable patients will be entered at each dose level for determination of MTD or recommended Phase 2 dose (RP2D) in Part A. Once the MTD or RP2D has been defined, up to 6 additional patients with relapsed/refractory solid tumors without heme restrictions may be enrolled to acquire PK data in a representative number of young patients (i.e. patients < 12 years old). Review of the enrollment rate into previous COG new agent studies indicates that 1-2 patients per month are available, which will permit enrollment and determination of the MTD or RP2D within 15-29 months if all dose levels are studied with six evaluable patients. A maximum of 51 patients is anticipated in Part A, which accounts for potential expansion to 12 patients at each dose level (see [Section 11.2.2](#)) and an inevaluable rate of 20%. **COMPLETE***

*Patients with medullary thyroid cancer may enroll to Part B of the study if there are no available slots on Part A. Part B will enroll concurrently at one dose level below that of solid tumor patients enrolled in Part A. If dose escalation has not yet occurred in Part A, patients in Part B will enroll at the initial dose level 1. Up to 6 patients may be enrolled onto each lagging dose level, for a maximum total of 18 evaluable patients in Part B. **COMPLETE***

*Once the MTD or RP2D is identified, intra-patient dose escalation will be allowed for patients with medullary thyroid cancer (MTC) remaining on study in cycles of therapy subsequent to cycle 1, provided that the patient did not experience dose-limiting toxicity (DLT) at the dose at which they began therapy. Patients who are one dose level below the MTD or RP2D can escalate to the MTD or RP2D. Patients who are more than one dose level below the MTD or RP2D can escalate one dose level per cycle until they reach the MTD or RP2D as long as they do not experience a DLT when escalating. **COMPLETE***

The recommended Phase 2 dose (RP2D) in patients with solid tumors was determined to be 40 mg/m² (see details in [Section 2.6](#)). In order to acquire additional PK data at this dose level, an additional 6 evaluable patients will be enrolled for a total of 12 evaluable patients at this dose level (6 < 12 years of age and 6 ≥ 12 years of age). If at any time cycle 1 DLT occurs in ≥ 33% of evaluable patients in Part A at 40 mg/m², the maximum tolerated dose will have been exceeded and the cohort will be closed to further enrollment. Part B will remain open with Part A at 40 mg/m² (the RP2D) to patients with MTC and may enroll a maximum of 6 evaluable patients (4 more in addition to the 2 already enrolled). Part B will close to enrollment when the PK cohort in Part A at 40 mg/m² has completed enrollment, or if 2 or more out of 6 evaluable patients in the Part B cohort experience cycle 1 DLT. Up to 12 additional patients will be enrolled for a maximum total of 41 patients in the study, which accounts for a 20% inevaluable rate. It should take an additional 3-6 months for completion of enrollment.

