2.5 Overview of Proposed Pediatric Study

This is a phase 1 limited dose-escalation study of XL184 (cabozantinib) in pediatric and adolescent patients with recurrent or refractory solid tumors including CNS tumors. The primary objectives of this study are to identify a maximum tolerated dose (MTD) or recommended phase 2 dose (RP2D), characterize the toxicity profile and describe the pharmacokinetics of XL184 in pediatric and adolescent patients with solid tumors.

Patients ages 2 to 18, inclusive, with refractory or recurrent solid tumors including CNS tumors will be eligible. Dosing will be based on body surface area (BSA) and rounded to nearest tablet to achieve the most accurate weekly doses. Doses on some days of the week may differ. Refer to dosing nomogram in [Appendix II](#) for details. XL184 will be administered orally at a starting dose of 30 mg/m²/day, which is roughly equivalent to the well tolerated 60 mg daily dose currently being evaluated in several adult studies. Doses will then be escalated to 40 mg/m² and 55 mg/m² in subsequent cohorts. One cycle will be 28 days in length and dosing will be continuous. The dose will be escalated using a rolling six design.

The maximum tolerated dose (MTD) will be determined from toxicities seen during the first cycle of therapy. The MTD will be the dose level immediately below the level in which ≥ 2 out of 2 to 6 patients experience a DLT. To be eligible for the toxicity endpoint, patients must have received $\geq 85\%$ of the prescribed study medication or have experienced a DLT during cycle 1.

THIS PROTOCOL IS FOR RESEARCH PURPOSES ONLY, SEE PAGE 1 FOR USAGE POLICY

Doses will not be escalated beyond 55 mg/m^2 . If an MTD is not identified, a recommended dose will be established based on tolerability, pharmacokinetic parameters and response, if applicable. After the MTD or recommended phase 2 dose is determined in Part A, an additional 6 patients may be enrolled in an expansion phase and treated at this dose to gain additional PK and toxicity data in the pediatric population. Every attempt will be made to treat a minimum of 6 patients < 12 years of age and 6 patients ≥ 12 years of age at the MTD or recommended phase 2 dose. Given the activity seen in patients with medullary thyroid carcinoma (MTC), an additional cohort for MTC patients (Part B) will be open for enrollment if slots are filled for Part A, with the goal of enrolling at least four patients with MTC.

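### Does the cap of 12 additional patients (41 in all) really cover a 20% inevaluable rate, and is 3-6 months long enough?

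*Combined protocol and SAP*

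**What the plan says.** Section 11.1 sets the enrolment that follows the choice of 40 mg/m² as the recommended dose. For Part A, "an additional 6 evaluable patients will be enrolled for a total of 12 evaluable patients at this dose level". Part B, for medullary thyroid cancer (MTC), "may enroll a maximum of 6 evaluable patients (4 more in addition to the 2 already enrolled"). The two cohorts are linked: "Part B will close to enrollment when the PK cohort in Part A" is fully enrolled, or sooner if the toxicity limit in Part B is reached. The overall cap is then given: "Up to 12 additional patients will be enrolled for a maximum total of 41 patients in the study, which accounts for a 20% inevaluable rate". The forecast follows: "It should take an additional 3-6 months for completion of enrollment".

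Four other places bear on the point:

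- Section 2.6 gives 29 patients enrolled as of January 2014.
- An earlier paragraph of Section 11.1, marked complete, says that experience in previous studies "indicates that 1-2 patients per month are available". It expects the dose to be found "within 15-29 months if all dose levels are studied with six evaluable patients".
- Section 2.5 describes Part B "with the goal of enrolling at least four patients with MTC".
- Section 11.2.1 has patients who are not evaluable for adverse effects replaced.

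**The concern.** An inevaluable rate is naturally a share of the patients enrolled. To end with a given evaluable number, one divides by one minus the rate. Here the plan appears to have multiplied by one plus the rate, which gives too few. If both cohorts fill, the cap falls just short of the rate that the sentence claims.

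The forecast in the next sentence seems to rest on a different basis. Six patients at 1-2 per month take exactly 3-6 months, with no time for replacements, although the cap beside it does include an allowance.

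If this mattered, the stakes would be an expansion that stops before both cohorts are full, and an enrolment period that overruns its forecast.

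**Working it through.** **Inputs.** Additional evaluable patients: 6 in Part A and at most 4 in Part B (Section 11.1). Already enrolled: 29 (Section 2.6). Inevaluable rate: 20% (Section 11.1). Accrual of 1-2 patients per month (earlier paragraph of Section 11.1).

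**1. Reproducing the plan's figure.** 6 + 4 = 10 evaluable; 10 × 1.2 = 12 additional; 29 + 12 = 41. Both stated numbers come out exactly. The earlier Part A maximum of 51 fits the same convention if it is built from 12 patients at each of three levels plus 6 for pharmacokinetics: (36 + 6) × 1.2 = 50.4, rounded up to 51. Division would give 42/0.8 = 52.5, so 53. That build-up is an inference.

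**2. The strict figure.** 10/0.8 = 12.5, so 13 additional and 29 + 13 = 42 in all. Twelve enrolled for 10 evaluable tolerates 2/12 = 16.7%. At a true 20%, 12 enrolled give 12 × 0.8 = 9.6 evaluable on average, a shortfall of 0.4 patient. Since 20% of 12 is 2.4, two inevaluable patients is also the nearest whole number to the stated rate.

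**3. Chance of reaching the ceiling.** Take each enrolled patient as evaluable independently with probability 0.8.

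- 12 enrolled: P(at least 10) = 66 × 0.8¹⁰ × 0.2² + 12 × 0.8¹¹ × 0.2 + 0.8¹² = 0.283 + 0.206 + 0.069 = 0.56.
- 13 enrolled: P(at least 10) = 0.75.

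**4. Chance of reaching the documented goals.** Part A needs 6. The goal of at least four MTC patients, with 2 already in Part B, needs 2 more. That is 6 + 2 = 8 evaluable; 8/0.8 = 10 enrolled, inside the cap of 12. With 12 enrolled, P(at least 8) = 0.93.

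**5. Enrolment time.** At 1-2 patients per month:

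| Patients to enrol | Months |
|---|---|
| 6 (Part A, no allowance) | 6/2 to 6/1 = 3-6 |
| 7.2 (6 × 1.2) | 3.6-7.2 |
| 8 (6/0.8 = 7.5, rounded up) | 4-8 |
| 12 (whole cap at that one rate) | 6-12 |

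Part A governs, because Part B closes with it. Eight patients would still finish within six months at 8/6 = 1.33 per month or faster.

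**6. Did the earlier forecast include an allowance?** 24 × 1.2 = 28.8, about 29 patients. At 2 and 1 per month that is 14.5 and 29 months, which fits the stated 15-29. The 24 could be three levels of six plus 6 pharmacokinetic patients. It could also be four levels of six, but Section 5.3.1 opens level -1 only if level 1 proves too toxic, so level 3 and level -1 would both be used only after de-escalation through every level. Three levels of six alone give 18 × 1.2 = 21.6 patients, about 11-22 months, which does not fit. So the earlier forecast probably included an allowance, but this does not show which rate lies behind the 3-6 months.

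**The case for a change.** The best case for a change is that the sentence claims a rate that its own numbers miss, and that correcting it costs nothing. The plan could keep 12 and 41 and call the allowance about 17%, and it could state the accrual rate or lengthen the forecast. Consistent use of the multiplying convention explains the number but does not make 12 enrolled yield 10 evaluable at 20%. The cap and the forecast also sit side by side on what look like different bases.

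The arithmetic of that case stands. Its weight does not, for three reasons:

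- Ten evaluable patients is the sum of a target and a ceiling, and the plan nowhere sets it as a goal. The 0.56 is the chance of filling every permitted place, not the chance of meeting an aim.
- A Part B that ends below its maximum is already part of the design, since it may close as soon as Part A is complete.
- The forecast names no rate. The 1-2 per month comes from earlier studies and a paragraph marked complete. By January 2014 the team had its own accrual of 29 patients to draw on, and no rate for MTC patients is given. That the forecast leaves out replacements is plausible, but it is an assumption.

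**Conclusion.** No change is needed. The cap reflects a rounding and inflation convention that is off by at most one patient: 12 against 13 additional, 41 against 42 in all, or an allowance of about 17% against 20%. That difference appears only if Part B takes all 4 further places. For the 8 evaluable patients that the plan actually aims for, the cap is enough at a full 20%.

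Nothing downstream depends on it. Section 11.5 makes the pharmacokinetic, response and survival analyses descriptive. The toxicity limits in Section 11.1 are set as a share or count of evaluable patients and do not use the cap. Rewording the rate or the forecast would alter no rule, analysis or conclusion, and the only change to conduct would be one more patient. Section 8.4 marks the pharmacokinetic work as complete, so a revised forecast would have little use.

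This rests on three assumptions: that the 2 patients already in Part B count toward the MTC goal, that evaluability is independent between patients at 0.8, and, for the forecast only, that 1-2 per month is the relevant rate.

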11.2 Definitions

11.2.1 Evaluable For Adverse Effects

Any patient who experiences DLT at any time during protocol therapy is considered evaluable for Adverse Effects. Patients without DLT who receive at least 85% of the prescribed dose per protocol guidelines and had the appropriate toxicity monitoring studies performed are also considered evaluable for Adverse Effects. Patients who are not evaluable for Adverse Effects at a given dose level will be replaced.

11.2.2 Maximum Tolerated Dose (Part A): COMPLETE

The MTD will be the maximum dose at which fewer than one-third of patients experience DLT (See [Section 5.5](#)) during Cycle 1 of therapy. In the event that two DLTs observed out of 6 evaluable patients are different classes of Adverse Effects (e.g. hepatotoxicity and myelosuppression), expansion of the cohort to 12 patients will be considered if all of the following conditions are met:

- *One of the DLTs does not appear to be dose-related*
- *The Adverse Effects are readily reversible*
- *The study chair, DVL statistician, DVL committee chair or vice chair, and IND sponsor all agree that expansion of the cohort is acceptable*

If fewer than 1/3 of patients in the expanded cohort experience dose-limiting toxicities, the dose escalation can proceed.

11.3 **Dose Escalation and Determination of MTD:- COMPLETE**

The rolling six phase 1 trial design will be used for the conduct of this study.¹⁷ Two to six patients can be concurrently enrolled onto a dose level, dependent upon (1) the number of patients enrolled at the current dose level, (2) the number of patients who have experienced DLT at the current dose level, and (3) the number of patients entered but with tolerability data pending at the current dose level. Accrual is suspended when a cohort of six has enrolled or when the study endpoints have been met.

Dose level assignment is based on the number of participants currently enrolled in the cohort, the number of DLTs observed, and the number of participants at risk for developing a DLT (i.e., participants enrolled but who are not yet assessable for toxicity). For example, when three participants are enrolled onto a dose cohort, if toxicity data is available for all three when the fourth participant entered and there are no DLTs, the dose is escalated and the fourth participant is enrolled to the subsequent dose level. If data is not yet available for one or more of the first three participants and no DLT has been observed, or if one DLT has been observed, the new participant is entered at the same dose level. Lastly, if two or more DLTs have been observed, the dose level is de-escalated. This process is repeated for participants five and six. In place of suspending accrual after every three participants, accrual is only suspended when a cohort of six is filled. When participants are inevaluable for toxicity, they are replaced with the next available participant if escalation or de-escalation rules have not been fulfilled at the time the next available participant is enrolled onto the study.

The following table provides the decision rules for enrolling a patient at (i) the current dose level (ii) at an escalated dose level, (iii) at a de-escalated dose level, or whether the study is suspended to accrual:

# Pts Enrolled	# Pts with DLT	# Pts without DLT	# Pts with Data Pending	Decision
2	0 or 1	0, 1 or 2	0, 1 or 2	Same dose level
2	2	0	0	De-escalate*
3	0	0, 1 or 2	1, 2 or 3	Same dose level
3	1	0, 1 or 2	0, 1 or 2	Same dose level
3	0	3	0	Escalate**
3	≥ 2	0 or 1	0 or 1	De-escalate*
4	0	0, 1, 2 or 3	1, 2, 3 or 4	Same dose level
4	1	0, 1, 2 or 3	0, 1, 2 or 3	Same dose level
4	0	4	0	Escalate**
4	≥ 2	0, 1 or 2	0, 1 or 2	De-escalate*
5	0	0, 1, 2, 3 or 4	1, 2, 3, 4 or 5	Same dose level
5	1	0, 1, 2, 3 or 4	0, 1, 2, 3 or 4	Same dose level
5	0	5	0	Escalate**
5	≥ 2	0, 1, 2 or 3	0, 1, 2 or 3	De-escalate*
6	0	0, 1, 2, 3, or 4	2, 3, 4, 5 or 6	Suspend
6	1	0, 1, 2, 3 or 4	0, 1, 2, 3 or 4	Suspend
6	0 or 1	5 or 6	0 or 1	Escalate**
6	≥ 2	0, 1, 2, 3 or 4	0, 1, 2, 3 or 4	De-escalate*

* If six patients already entered at next lower dose level, the MTD has been defined.

** If final dose level has been reached, the recommended dose has been reached.

If two or more of a cohort of up to six patients experience DLT at a given dose level, then the MTD has been exceeded and dose escalation will be stopped (see [Section 11.2.2](#) for exception to rule).

In addition to determination of the MTD or RP2D, a descriptive summary of all toxicities will be reported.

11.4 Inclusion of Children, Women and Minorities

The study is open to all participants regardless of gender or ethnicity. Review of accrual to past COG studies of new agents demonstrates the accrual of both genders and all NIH-identified ethnicities to such studies. Efforts will be made to extend the accrual to a representative population, but in a Phase 1 trial which will accrue a limited number of patients, a balance must be struck between patient safety considerations and limitations on the number of individuals exposed to potentially toxic or ineffective treatments on the one hand and the need to explore gender, racial, and ethnic aspects of clinical research on the other. If differences in outcome that correlate to gender, racial, or ethnic identity are noted, accrual may be expanded or additional studies may be performed to investigate those differences more fully.

11.5 Pharmacokinetic and Correlative Studies and Response Analysis

A descriptive analysis of pharmacokinetic (PK) parameters of XL184 will be performed to define systemic exposure, drug clearance, and other pharmacokinetic parameters. The PK parameters will be summarized with simple summary statistics, including means, medians, ranges, and standard deviations (if numbers and distribution permit).

While the primary aim of this study is to evaluate the toxicity of XL184 patients will have disease evaluations performed as indicated in [Section 8.1](#). Disease response will be assessed according to RECIST criteria for patients with solid tumors, and will be reported descriptively. Overall survival from study entry will also be assessed and summarized using the Kaplan-Meier method at the 6 month, 12 month, and 5 year timepoints.

All these analyses will be descriptive and exploratory and hypotheses generating in nature.

12.0 EVALUATION CRITERIA

12.1 Common Terminology Criteria for Adverse Events (CTCAE)

The descriptions and grading scales found in the revised NCI Common Terminology Criteria for Adverse Events (CTCAE) version 4.0 will be utilized for AE reporting. All appropriate treatment areas should have access to a copy of the CTCAE version 4.0. A copy of the CTCAE version 4.0 can be downloaded from the CTEP website (<http://ctep.cancer.gov>).

12.2 Response Criteria for Patients with Solid Tumors

See the table in [section 8.0](#) for the schedule of tumor evaluations. In addition to the scheduled scans, a confirmatory scan should be obtained 21-28 days following initial documentation of objective response.

Response and progression will be evaluated in this study using the revised Response Evaluation Criteria in Solid Tumors (RECIST) guideline (version 1.1) [Eur J Ca 45:228-247, 2009]. Key points are that 5 target lesions are identified and that changes in the *largest* diameter (unidimensional measurement) of the tumor lesions but the *shortest* diameter of malignant lymph nodes are used in the RECIST v 1.1 criteria.

